13.3 Sample Size/Accrual Rates

The primary endpoint of the study is the change in FACIT-F score for patients receiving melatonin and the same for patients receiving placebo. In a prior study of a pharmacological intervention for cancer-related fatigue ([44](#)), the expected mean and SD of the overall change in FACIT-F score in the placebo group was 13 and SD was 14.78. We assume the same SD for the melatonin subgroup and a clinically meaningful difference is deemed to be a half SD difference which is approximately 7 units. Based on these findings and using a two-sided t-test at 5% level of significance, we would need 71 patients in each of the placebo and melatonin groups for 80% power. Our target cohort size is, therefore, 142 patients.

Compliance is expected to be very high, and the drop-out rate is expected to be minimal. As a result, no adjustment of the sample size is done to accommodate drop outs or lack of compliance; however, the patients dropping out before the completion of the post treatment questionnaire will be replaced.

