13 STATISTICAL CONSIDERATIONS

13.1 Study Design and Analysis

This is a double-blind, placebo-controlled trial randomizing participants to 20 mg oral melatonin at night throughout the course of their RT plus an additional 2 weeks. Eligible patients will be electronically randomized on a 1:1 ratio within each stratum to melatonin treatment or placebo. Investigational pharmacists will dispense either melatonin or placebo capsules according to a computer-generated random assignment list. The allocation scheme would keep the allocation ratio approximately equal across all of the strata. Stratification is done according to treatment duration (less than 3 weeks; equal to or greater than 3 weeks) and prior chemotherapy (yes/no). Treatment allocation will be concealed from patients, investigators, and study coordinators enrolling the participants. The statistical collaborator will be unblinded and provide the randomization list to the pharmacy. Interim results needed for Data and Safety Monitoring Committee (DSMC) review will be provided by the research nurse in a blinded manner; however, the statistician can unblind groups to the DSMC if there is a concern. The primary investigators and other collaborators would remain blinded.

The primary hypothesis of no change in fatigue will be tested using the ANOVA F-test after adjusting for duration of RT (binary) and prior chemotherapy. Stratified randomization will be used to keep the groups balanced; however, statistical model will also be adjusting for them. The final hypothesis test level will be adjusted using O'Brien Fleming spending function for type I error. Details of interim analysis are provided in [Section 13.6](#).

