13.6 Interim Analysis

An interim analysis will be performed once one-half of the target patient sample size is accrued and evaluable. The unified family method with $\rho=0.3$ (45) will be used as the spending function to determine the rejection boundary, which is a modified version of the O'Brien Fleming method. As computed by SAS proc Seqdesign, 36 evaluable patients in each arm will be needed to perform this analysis and a standardized absolute z value of 2.49 will be needed to reject the null hypothesis at the interim stage. To maintain a 5% level of significance, the final analysis will be done at the 0.037 level, which is equivalent to using an absolute z score of 2.02 for rejecting the null hypothesis. The sponsor-investigator will remain blinded to the interim analysis, although it will be made available to the DSMC.

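### The 80% power in 13.3 belongs to a single-look t-test; the two-look design in 13.6 gives about 76–79.5% at 7 units, depending on which of its conflicting final levels is used

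*Combined protocol and SAP*

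**What the plan says.** Section 13.3 sizes the trial "using a two-sided t-test at 5% level of significance". Its SD comes from an earlier trial, where the change "in the placebo group was 13 and SD was 14.78", and the target is set this way: "a clinically meaningful difference is deemed to be a half SD difference which is approximately 7 units". The result is that "we would need 71 patients in each of the placebo and melatonin groups for 80% power", 142 in total, and "no adjustment of the sample size is done to accommodate drop outs or lack of compliance" because drop-outs are replaced. Section 13.3 does not mention an interim analysis.

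Section 13.1 plans a different final test: the primary hypothesis is "tested using the ANOVA F-test after adjusting for duration of RT (binary) and prior chemotherapy".

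Section 13.6 adds one efficacy look at half the target sample, using the unified family with rho = 0.3. For early rejection it says that "36 evaluable patients in each arm will be needed to perform this analysis and a standardized absolute z value of 2.49 will be needed". It then sets the final test at 0.037, describes that as the same as |z| 2.02, and says this preserves 5% overall. The protocol summary (Statistical Methodology) instead gives 4.5% for the final F-test.

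**The concern.** An early chance to reject, combined with a stricter final threshold, normally costs a little power. A sample size calculated for a single test at the full 5% has no room for that cost. If 13.3 was never updated for 13.6, the stated 80% is not the power of the planned design.

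The final threshold is also given in three forms that do not agree, so neither power nor type I error is fixed until one is chosen. In addition, 2.49 and 2.02 are normal quantiles while the named test is an F-test. The plan does not say whether they are to be read as p-values or compared directly with the test statistic.

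**Working it through.** **Inputs.** Difference 7, SD 14.78, 71 per arm and two-sided 5% (13.3); 1:1 allocation and adjusted ANOVA (13.1); look at 36 per arm, |z| 2.49, final 0.037 or |z| 2.02, rho = 0.3 (13.6); final 4.5% (protocol summary).

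**1. Reproduce 13.3.** Standardised drift = 7 / (14.78 × √(2/71)) = 7 / 2.481 = 2.82. The noncentral t-test has power 80.02% at 71 per arm, and the exact solution is 70.96 per arm. By normal theory the single-look power is 80.6%. So 71 is the single-look answer with no margin.

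**2. Reproduce the boundary in 13.6.** With z_k = C × t_k^(−0.3), looks at information 0.5 and 1, and overall two-sided error 0.05, C = 2.021. The interim cut-off is 2.021 × 0.5^(−0.3) = 2.488. These are the 2.49 and 2.02 in the text. For normal statistics they spend 5.00% in total.

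**3. Convert the final rules to one scale.** Two-sided p for |z| 2.02 is 0.0434. A level of 0.037 is |z| 2.09, and 0.045 is |z| 2.00. At the interim, |z| 2.49 is p = 0.0128.

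**4. Two-look power and error.** Power = 1 − P(|Z1| < c1 and |Z2| < c2), where (Z1, Z2) is bivariate normal with means 2.82 × √0.5 and 2.82 and correlation √0.5. Type I error uses zero means. The planned test was also simulated as an ANOVA with two binary covariates (assumed prevalences 0.3 and 0.5, no prognostic effect), looking at 36 and 71 per arm. Interim cut-off 2.49 throughout:

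| Final rule | Power, normal | Power, ANOVA statistic vs z cut-offs | Power, ANOVA p-values | Type I, normal | Type I, ANOVA statistic vs z cut-offs | Type I, ANOVA p-values |
|---|---|---|---|---|---|---|
| z 2.02 (p 0.0434) | 79.5% | 78.8% | 78.2% | 5.0% | 5.4% | 5.0% |
| 0.037 (z 2.09) | 77.7% | 77.0% | 76.3% | 4.4% | 4.8% | 4.4% |
| 0.045 (z 2.00) | 79.9% | 79.3% | 78.6% | 5.2% | 5.5% | 5.2% |

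An unadjusted t-test with final 2.02 gives 78.9% power and 5.0% error on the p-value scale, and 5.3% error against the z cut-offs.

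**5. Like-for-like cost of the interim look.** Normal theory: 80.6 − 79.5 = 1.1 points at 2.02, and 80.6 − 77.7 = 2.9 points at 0.037. For 80% power at 7 units the two-look design needs 72–74 per arm at 2.02 and 76 at 0.037.

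**6. Why the scale matters at the interim.** With 72 patients and four model terms there are 68 residual degrees of freedom. P(|Z| > 2.49) = 0.0128, but P(|t68| > 2.49) = 0.0152.

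**7. Sensitivity.** At half of 14.78 = 7.39 units, two-look power is 82.6–83.6% with 2.02 and 80.9–82.0% with 0.037. If the two adjustment factors explained 2% or 5% of the variance (an assumption), normal-theory power at 7 units would be 80.3% or 81.5% with 2.02, and 78.5% or 79.8% with 0.037.

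**The case against.** The strongest reply is that the shortfall is small and depends on rounding. Section 13.3 defines the target as half an SD, and 7 is its rounded value; at 7.39 the two-look design exceeds 80% under either rule in 13.6. Modest prognostic value in the stratification factors would also recover the loss at 2.02. This stands as a limit on the size of the point. It does not rescue the statement in 13.3, because 71 per arm is the answer for 7 units and not for 7.39, where about 64 per arm would do (63.77). Nor does 13.3 claim any gain from adjustment.

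Two stronger readings are tempting and should not be made.

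- A reader might infer that the plan has a type I error of 5.3% together with 77% power. No single rule gives both. Power near 77% goes with 0.037, where error is 4.4–4.8%. Error of 5.3–5.4% goes with 2.02 and a direct comparison of root-F or t with the normal cut-offs, where power is about 79%. The plan does not prescribe that comparison, and it states the final test as a significance level, which suits an F-test p-value.
- A reader might infer from 36 per arm that the interim was designed for 72 per arm. Half of 142 is 71, or 35.5 per arm, which also rounds up to 36, so the figure does not show a second design.

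**Conclusion.** The point holds in a limited form. The 80% in 13.3 is the power of a test the trial will not perform. Using the 2.02 boundary that fits rho = 0.3, the shortfall at 7 units is 0.5–1.8 points below 80%, which would not by itself justify more patients. At the written 0.037 it is 2.3–3.7 points. These figures assume SD 14.78 in both arms, no covariate gain and all 71 per arm evaluable.

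The inconsistency in the final level matters more. The 0.037 and |z| 2.02 in 13.6 are different rules, and the 4.5% in the summary is a third. On the p-value scale the 4.5% rule, with 2.49 at the interim, takes overall error slightly above 5% (about 5.1–5.2%), while 0.037 leaves part of the 5% unused. Exceeding 5% under the 2.49/2.02 boundaries depends on how the cut-offs are applied; it is an ambiguity to close and not an established error rate of the plan.

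**What to change.** Keep 142 patients and make three text changes.

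- **13.6, interim:** state the boundary as a two-sided p-value from the adjusted ANOVA, p ≤ 0.0128 (equivalent to |z| 2.49).
- **13.6 and protocol summary, final:** replace both 0.037 and 4.5% with the level that matches the stated rho = 0.3 boundary, two-sided ANOVA p ≤ 0.0434 (|z| 2.02). Overall error is then 5.0%.
- **13.3:** say that 71 per arm gives about 79% power for 7 units under the two-look design of 13.6. If 0.037 is kept instead, say about 77%, remove the claimed equivalence with |z| 2.02, and put 0.037 in the summary.

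The cost is a few sentences and a slightly less favourable stated power. No patients are added.

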13.4 Stratification Factors

The patients will be stratified according to duration of radiation treatment (less than 3 weeks; equal to or greater than 3 weeks) and prior chemotherapy (yes/no). Analysis of the primary hypothesis will be adjusted for the stratification factors. However, the sample size computation used only the data available from one strata as there is little knowledge about the effect size in each individual strata. Target power is kept at 80% to protect against possible lack of separation in some strata, keeping the target sample size in a feasible range.

13.5 Analysis of Secondary Endpoints

Secondary analysis of each of the subscales and ESAS scale for each strata will be reported using a 2 sample t-test with necessary adjustment needed for normality of the scores. Cohorts will be tested for homogeneity at baseline with respect to each of the scales. Other secondary outcomes will be summarized in the overall cohort, as well as in each subgroup of patients. Exploratory analysis will be done to identify the patient subgroup with relatively high effect and low effect.

13.6 Interim Analysis

An interim analysis will be performed once one-half of the target patient sample size is accrued and evaluable. The unified family method with $\rho=0.3$ (45) will be used as the spending function to determine the rejection boundary, which is a modified version of the O'Brien Fleming method. As computed by SAS proc Seqdesign, 36 evaluable patients in each arm will be needed to perform this analysis and a standardized absolute z value of 2.49 will be needed to reject the null hypothesis at the interim stage. To maintain a 5% level of significance, the final analysis will be done at the 0.037 level, which is equivalent to using an absolute z score of 2.02 for rejecting the null hypothesis. The sponsor-investigator will remain blinded to the interim analysis, although it will be made available to the DSMC.

14 DATA AND SAFETY MONITORING PLAN (DSMP)

The DSMP for this study will consist of the following 3 elements:

14.1 Study Team

The study team minimally consists of the sponsor-investigator, the research nurse, the clinical research associate, and the study biostatistician. While patients are on treatment, the sponsor-investigator, the research nurse, and the clinical research associate will meet at least monthly, and will meet at least quarterly with the study biostatistician, to review study status. This review will include, but not be limited to, reportable AEs and UPs, and an update of the ongoing study summary that describes study progress in terms of the study schema. The appropriateness of further patient enrollment and the specific intervention for

a next patient enrollment are addressed. All meetings including attendance are documented.

14.2 Monitoring and Auditing

14.2.1 MCC Compliance Office

Compliance specialists in the MCC Compliance Office will provide ongoing monitoring and auditing for this trial.

14.2.2 Data and Safety Monitoring Committee

The study will be reviewed by the MCC Data and Safety Monitoring Committee (DSMC) initially according to the risk level specified by the MCC Protocol Review and Monitoring Committee (PRMC) and then according to a schedule based on study status and quality indicators. The DSMC reviews reports of the sponsor-investigator/study team and the MCC Compliance Office focusing on data integrity and patient safety.

15 REGULATORY COMPLIANCE AND ETHICS

15.1 Ethical Standard

This study will be conducted in conformance with the principles set forth in *The Belmont Report: Ethical Principles and Guidelines for the Protection of Human Subjects of Research* (US National Commission for the Protection of Human Subjects of Biomedical and Behavioral Research, April 18, 1979).

15.2 Regulatory Compliance

This study will be conducted in compliance with:

- The protocol
- Federal regulations, as applicable, including: 21 CFR 50 (Protection of Human Subjects/Informed Consent); 21 CFR 56 (Institutional Review Boards); 21 CFR 312 (IND Application); and 45 CFR 46 Subparts A (Common Rule), B (Pregnant Women, Human Fetuses and Neonates), C (Prisoners), and D (Children)

15.3 Institutional Review Board

Each participating institution must provide for the review and approval of this protocol and the associated informed consent documents and recruitment material by an appropriate IRB registered with the Office for Human Research Protections (OHRP). Any amendments to the protocol or consent materials must also be approved. In the United States and in other countries, only institutions holding a current US Federalwide Assurance issued by OHRP may participate.

15.4 Informed Consent Process

Informed consent is a process that is initiated prior to the individual's agreeing to participate in the study and continues throughout the individual's study participation. Extensive discussion of risks and possible benefits of this therapy will be provided to the patients and their families. Consent forms describing in detail the study interventions/ products, study procedures, and risks are given to the patient and written documentation of informed consent is required prior to starting intervention/administering study product. Consent forms will be IRB-approved and the patient will be asked to read and review the document. Upon reviewing the document, the investigator or research nurse will explain the research study to the subject and answer any questions that may arise. The subject will sign the informed consent document prior to any procedures being done specifically for the study. The patients should have the opportunity to discuss the study with their surrogates or think about it prior to agreeing to participate. The patients may withdraw consent at any time throughout the course of the trial. A copy of the informed consent document will be given to the subjects for their records. The rights and welfare of the patients will be protected by emphasizing to them that the quality of their medical care will not be adversely affected if they decline to participate in this study.

15.5 Patient Confidentiality and Access to Source Documents/Data

Patient confidentiality is strictly held in trust by the participating investigators and their staff. This confidentiality includes the clinical information relating to participating patients, as well as any genetic or biological testing.

The study protocol, documentation, data, and all other information generated will be held in strict confidence. No information concerning the study or the data will be released to any unauthorized third party without prior written approval of the sponsor-investigator.

The sponsor-investigator will allow access to all source data and documents for the purposes of monitoring, audits, IRB review, and regulatory inspections.

The study monitor or other authorized representatives of the sponsor-investigator may inspect all documents and records required to be maintained by the investigator, including but not limited to, medical records (office, clinic, or hospital) and pharmacy records for the patients in this study. The clinical study site will permit access to such records.

16 DATA HANDLING AND RECORD KEEPING

16.1 Data Management Responsibilities

The sponsor-investigator is responsible for: (i) the overall conduct of the investigation; (ii) ongoing review of trial data including all safety reports; and (iii) apprising participating sites of any UPs.

The responsible investigator at each site is responsible for: (i) the data management at his or her site; and (ii) reporting SAEs and UPs as required in [Section 8](#).

Any laboratory conducting correlative studies must maintain the laboratory records and documentation (laboratory notebooks, laboratory protocols, print-outs, recordings, photographs, etc.).

16.2 Source Documents

Source documents for clinical information (patient history, diagnosis, clinical and diagnostic test reports, etc.) are maintained in the patient's clinical file. Source documents for the correlative studies are maintained in the laboratory conducting the study.

16.3 Case Report Forms

MCC OnCore data management will provide standard electronic case report forms (eCRFs) and create study-specific eCRFs to capture all the information required by the protocol. The eCRFs will be approved by the study team to ensure the most effective data acquisition. All information on eCRFs will be traceable to the source documents which are generally maintained in the patient's file. All eCRFs should be completed and available for collection within a timely manner, preferably no more than 14 days after the patient's visit.

16.4 Study Record Retention

As applicable, study records will be maintained a minimum of 5 years beyond: (i) the publication of any abstract or manuscript reporting the results of the protocol; (2) the submission of any sponsored research final report; or (iii) submission of a final report to clinicaltrials.gov.

18 APPENDIX 1. FACIT-F SCALE

The FACIT-F scale is given on the following 3 pages.

FACIT-F (Version 4)

Patient's Initials: _____

Date: _____

Study ID #: _____

Time Point: _____

Below is a list of statements that other people with your illness have said are important. **Please circle or mark one number per line to indicate your response as it applies to the past 7 days.**

PHYSICAL WELL-BEING		Not at all	A little bit	Some- what	Quite a bit	Very much
GP1	I have a lack of energy	0	1	2	3	4
GP2	I have nausea	0	1	2	3	4
GP3	Because of my physical condition, I have trouble meeting the needs of my family	0	1	2	3	4
GP4	I have pain	0	1	2	3	4
GP5	I am bothered by side effects of treatment	0	1	2	3	4
GP6	I feel ill	0	1	2	3	4
GP7	I am forced to spend time in bed	0	1	2	3	4

SOCIAL/FAMILY WELL-BEING		Not at all	A little bit	Some- what	Quite a bit	Very much
GS1	I feel close to my friends	0	1	2	3	4
GS2	I get emotional support from my family	0	1	2	3	4
GS3	I get support from my friends	0	1	2	3	4
GS4	My family has accepted my illness	0	1	2	3	4

FACIT-F (Version 4)

GS5	I am satisfied with family communication about my illness	0	1	2	3	4
					
GS6	I feel close to my partner (or the person who is my main support)	0	1	2	3	4
					
Q1	Regardless of your current level of sexual activity, please answer the following question. If you prefer not to answer it, please mark this box  and go to the next section.					
GS7	I am satisfied with my sex life	0	1	2	3	4

FACIT-F (Version 4)

Patient's Initials: _____

Study ID #: _____

Please circle or mark one number per line to indicate your response as it applies to the past 7 days.

EMOTIONAL WELL-BEING

Not at all A little bit Some-what Quite a bit Very much

GE1	I feel sad	0	1	2	3	4
GE2	I am satisfied with how I am coping with my illness	0	1	2	3	4
GE3	I am losing hope in the fight against my illness	0	1	2	3	4
GE4	I feel nervous	0	1	2	3	4
GE5	I worry about dying	0	1	2	3	4
GE6	I worry that my condition will get worse	0	1	2	3	4

FUNCTIONAL WELL-BEING

Not at all A little bit Some-what Quite a bit Very much

GF1	I am able to work (include work at home)	0	1	2	3	4
GF2	My work (include work at home) is fulfilling	0	1	2	3	4
GF3	I am able to enjoy life	0	1	2	3	4
GF4	I have accepted my illness	0	1	2	3	4
GF5	I am sleeping well	0	1	2	3	4
GF6	I am enjoying the things I usually do for fun	0	1	2	3	4

FACIT-F (Version 4)

GF7

I am content with the quality of my life right now 0 1 2 3 4

FACIT-F (Version 4)

Patient's Initials: _____

Study ID #: _____

Please circle or mark one number per line to indicate your response as it applies to the past 7 days.

	ADDITIONAL CONCERNS	Not at all	A little bit	Some- what	Quite a bit	Very much
HI7	I feel fatigued	0	1	2	3	4
HI12	I feel weak all over	0	1	2	3	4
An1	I feel listless ("washed out")	0	1	2	3	4
An2	I feel tired	0	1	2	3	4
An3	I have trouble starting things because I am tired	0	1	2	3	4
An4	I have trouble finishing things because I am tired	0	1	2	3	4
An5	I have energy	0	1	2	3	4
An7	I am able to do my usual activities	0	1	2	3	4
An8	I need to sleep during the day	0	1	2	3	4
An12	I am too tired to eat	0	1	2	3	4
An14	I need help doing my usual activities	0	1	2	3	4
An15	I am frustrated by being too tired to do the things I want to do	0	1	2	3	4
An16	I have to limit my social activity because I am tired	0	1	2	3	4

FACIT-F (Version 4)

19 APPENDIX 2. ESAS SCALE

The ESAS scale is provided on the following page. The “Other problem,” listed as the last optional item on the scale, will be sleep. Best sleep=0; worst possible sleep=10.

**Edmonton Symptom Assessment System:
Numerical Scale
Regional Palliative Care Program**

Patient's Initials: _____

Study ID #: _____

Date: _____

Time Point: _____

Please circle the number that best describes:

No pain 0 1 2 3 4 5 6 7 8 9 10 Worst possible pain

Not tired 0 1 2 3 4 5 6 7 8 9 10 Worst possible tiredness

Not nauseated 0 1 2 3 4 5 6 7 8 9 10 Worst possible nausea

Not depressed 0 1 2 3 4 5 6 7 8 9 10 Worst possible depression

Not anxious 0 1 2 3 4 5 6 7 8 9 10 Worst possible anxiety

Not drowsy 0 1 2 3 4 5 6 7 8 9 10 Worst possible drowsiness

Best appetite 0 1 2 3 4 5 6 7 8 9 10 Worst possible appetite

Best feeling of 0 1 2 3 4 5 6 7 8 9 10 Worst possible feeling
wellbeing

No shortness of 0 1 2 3 4 5 6 7 8 9 10 Worst possible
breath

Best sleep 0 1 2 3 4 5 6 7 8 9 10 Worst possible sleep

Initials _____

Complete by (check one)

Patient

Caregiver

Caregiver assisted

Date _____ Time _____

